5.3. IC Treatment Responders

In this study each subject is served as his/her control when the IC treatment is given as a visualization aid when determining ureter patency, IC treatment responder, hence, could be defined based on the conspicuity score following IC and saline.

To determine proportion of subjects meeting the responder definition in conspicuity score following IC treatment the blinded central reviewer's assessment will be used. A subject is a responder when there is ≥ 1 point improvement in the conspicuity scores following the IC vs saline treatment (IC – Saline ≥ 1) and the conspicuity score following the IC treatment is (3, 4, or 5). The responder criteria will be assessed separately for each ureter for each subject.

Since the responder definition will be defined for each ureter per subject, when a subject has missing data, the corresponding responder variable cannot be defined. The primary analysis will exclude all subjects that the responder definition cannot be derived due to missing data; this will be referred to as the Observed Analysis.

To assess the impact of missing data, a sensitivity analysis will be conducted. In this sensitivity analysis, the responder variable will be set to 'No' for those that cannot be derived due to missing data. This analysis will represent the worst-case scenario for this analysis.

Summary tables (Tables 14.2.3.1 and 14.2.3.2) will provide number (%) subjects meeting the responder definition in the following categories: overall (left or right), left ureter, right ureter, or both ureters for each IC dose and overall; 95% confidence intervals based on normal approximation will also be provided, along with the difference in proportion of responders between the IC high dose vs IC low dose.

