2. OVERVIEW OF STUDY OBJECTIVES AND ASSESSMENTS

The primary objective of this study is to determine whether the use of Indigo Carmine 0.8% Injection, USP solution for injection (IC) provides a visualization advantage compared to saline when used as an aid in the determination of ureteral patency. Visualization will be measured by a 5-point conspicuity score as follows:

- 1 = No jet observed
- 2 = Weak jet, little color contrast
- 3 = Color contrast or significant jet flow
- 4 = Strong jet flow with good color contrast
- 5 = Strong jet flow with striking contrast in color

Secondary objectives are to assess:

1. To evaluate the safety profile of IC when used as an aid in the determination of ureteral patency.
2. To determine physicians' overall satisfaction with the IC treatment by assessing the proportion of surgeons who agree using the 5-point Physician Satisfaction Agreement Scale (PSAS) with the statement:

“Compared to the saline treatment, my ability to assess ureter patency was improved after the addition of IC.”

- 1. Strongly Agree
- 2. Agree
- 3. Neither Agree nor Disagree
- 4. Disagree
- 5. Strongly Disagree

A surgeon's evaluation is considered satisfactory if the rating is either a 1 (strongly agree) or 2 (agree).

3. To determine proportion of responders. To determine proportion of subjects meeting the responder definition in conspicuity score following IC treatment based on the blinded central reviewer's assessment. A subject is a responder when there is ≥ 1 point difference in the conspicuity score following the IC vs saline treatment (IC – Saline ≥ 1) and the conspicuity score following the IC treatment is (3, 4, or 5). The responder criteria will be assessed separately for each ureter for each subject.

4. To describe the time to visualization (TTV) of blue color in the ureteral jets flow following IC treatment when used as a visualization aid during urological and gynecological surgical procedures
5. To determine the IC pharmacokinetic profile in a subset of subjects from 2 investigational sites.
6. An exploratory comparison will be done on the difference between the IC high dose vs IC low dose. Surgeons will be blinded to the dose of IC.

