The videos will be sent to a central imaging group that will pool and blind the videos. Videos will then be assessed by 2 blinded central reviewers for assessment of ureteral patency using the 5-point conspicuity score criteria. The 2 independent central reviewers will provide 2 conspicuity scores (1 for left ureter and 1 for right ureter) for each video. The consistency between the two reviewers will be checked; the two reviewers will be considered consistent if their scores for the corresponding ureter is (+/-) 1 point of a given video. In this case, the average score across the two reviewers will be the final score for efficacy analysis. Otherwise, a third reviewer (a judicator) will step in and will review this video. The scores from this third reviewer will be the final score for this video for efficacy analysis.

After the procedure, the surgeon performing the procedure will provide his/her overall satisfaction assessment by rating his/her agreement with the statement “Compared to the saline

treatment, my ability to assess ureteral patency was improved after the addition of IC” using the PSAS: 1=Strongly Agree, 2=Agree, 3=Neither Agree nor Disagree, 4=Disagree, 5=Strongly Disagree.

In addition, after the procedure the surgeon will also review the videos of his/her patients and will provide the conspicuity scores for each ureter after each treatment using the same 5-point conspicuity score criteria. The surgeons score will be utilized for conspicuity score concordance analysis.

In a subset of subjects from 2 sites (about 16 subjects), subjects will be consented to participate in the pharmacokinetic (PK) portion of the study. Once consented, 13 blood samples will be taken from each subject at the scheduled timepoints post IC treatment for PK analysis. Urine collection will occur by a voided sample within 1 hour prior to the surgery and post IC injection for the following time periods 0-2 hours (including any urine drained during surgery), 2-6 hours, and 6-12 hours. The first post-op stool will also be collected for analysis in this PK group.

All treated subjects will have a follow-up visit 7 to 30 days (\pm 2 days) after the procedure. A final telephone follow-up call will occur on Day 30 (\pm 2 days) in subjects who have the follow-up visit before Day 28.

Safety assessments will include monitoring of AEs during and post the procedure, clinical laboratory tests, 12-Lead ECG, and vital sign measurements.

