3.8.2. IC Treatment Responders

A responder (Yes/No) variable will be derived for each subject by comparing the conspicuity score following IC treatment vs the conspicuity score after saline treatment. When there is ≥ 1 point improvement (IC – Saline) in the conspicuity score and the conspicuity score following the IC treatment is (3, 4, or 5) for a subject, this subject is considered a responder of the IC treatment. The responder assessment will be performed for each ureter separately.

3.8.3. Time to Visualization (TTV) of Blue Color in the Ureteral Jets After IC Administration

Each randomized subject is expected to receive 1 dose of saline and 1 dose of IC; time of each injection, including start time and completion time, will be recorded as HHMMSS (hour, minute, and second). **TTV event is assessed only after IC treatment within 10 minutes after the injection start.** Time when this event occurred after IC injection will be captured as HHMMSS. Therefore, TTV following each injection will be derived as follows.

TTV (minutes) = (time when adequate visualization occurs - start time of injection) / 60

If the adequate visualization of blue color in the ureter jet flow at an ureteral orifice following IC injection for a subject did not occur for any reason, this subject will be censored for this analysis. The censored time will be set to 10 minutes.

TTV will be derived for each subject following IC injection for each ureter separately.

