3.8.3.1. Missing Data Imputation Rules for TTV

In order to calculate TTV, the injection start time and time when blue color is adequate visualized in the ureter jet flow must be present. Although the clinical team will make the best effort to eliminate missing or partial time, mistakes could occur. The following rules will be implemented should a subject had missing or partial injection time or time when blue color in the ureter jet flow is adequately visualized.

1. When the injection start time is missing or partial

- 1) If injection start time is missing but the completion time is present, the missing start time will be set to be the same as the injection completion, and vice versa.
- 2) If the hour and minutes are non-missing but the seconds are missing for injection start time, the first second (01) will be assigned to the injection time.
- 3) Otherwise the median elapsed time (defined as time between surgery start time and injection start time) in the study across all subjects who did not have missing data will be used to impute the missing time. That is, the missing injection start time will be set as (Surgery start time + median elapsed time).

The rules will be implemented based on this order.

2. When event occurred but the time is missing or partial

A subject is considered to have had this event when the conspicuity score is 4 or higher per central reader score for this ureter. When a subject has this event but the time when the event occurred is missing, the following rules will be applied.

- 1) If the time is partial (i.e., only the seconds are missing), the first second (01) will be assigned.
- 2) If the time is missing, the subject will not be censored for this endpoint. The missing time, however, will be assigned to 10 minutes after the injection start time.
- 3) This event will be considered as an important protocol deviation. The subject will be excluded from the efficacy PP analysis set. A sensitivity analysis may be performed for the TTV endpoint based on the efficacy PP analysis set.

If a subject had issue(s) with a ureter initially this subject will be censored for this analysis regardless if the issue(s) is or is not fixed during the procedure.

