5.1. Conspicuity Score from the Central Readers

In this study each subject will serve as his/her own control and each subject will have repeated measures from the same treatment (1 from the left and 1 from the right ureter); therefore, each subject is expecting to contribute 4 observations for conspicuity endpoint. The recording videography will be read by the surgeon (who is unblinded for treatment and blinded for IC dose) and by two center readers who is blinded to the treatment (Saline vs IC) and IC dose. The score from the central readers will be the source for the primary endpoint analysis and the conspicuity score provided by the surgeons will be utilized for concordance analysis (see [Section 5.5](#) for details).

There will be 2 central reviewers to watch each video after the videos are blinded. The ratings are acceptable for consistency if the scores from the two independent reviewers for a ureter under the same treatment are within (+/-) 1 point. In this case, the average score across the two reviewers will be the final score from the central reader. Otherwise, a third independent reviewer (a judicator) will review the same video and this judicator's score will be the final score from the central reader.

As indicated earlier in [Section 3.7](#) the summary table for this endpoint will include 3 treatment groups, namely IC High Dose, IC Low Dose, and Saline Group. It is expected that the sample size (n) for the Saline group will be twice the size of the sample size for the IC High dose and IC Low Dose.

The treatment effect on the conspicuity score will be evaluated using a Generalized Estimating Equation (GEE) for Repeated Measures to control for the intra-subject correlation by fitting a proportional odds model to evaluate the treatment effect. A full model (**Model 1**) will provide the chi-square tests (Score Statistics for Type 3 GEE Analysis) for the effects from treatment (IC High dose / IC Low dose, Saline), ureter (left side ureter vs right side ureter), and treatment*ureter interaction on the response based on multi-normal distribution for an ordinal

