5.2. PSAS with IC Treatment

Each subject will have 1 PSAS score. Ratings in the PSAS with the IC treatment will be tabulated (**Table 14.2.2**) by treatment (IC High dose, IC Low dose, and overall (pooled across high dose and low dose) with number (%) subjects in each rating category and overall satisfactory.

Two-sided 95% confidence intervals on proportion of physicians who are satisfied (with ratings 1 or 2) will be derived using the Wilson confidence limits for the binomial proportion. This is also known as score confidence limits. The Wilson interval has been shown to have better performance than the Wald interval and the exact (Clopper-Pearson) interval (SAS Users' manual).

A binomial 1-way proportion approach will be used to examine that $\geq 50\%$ of the physicians are satisfied with the IC treatment (a superiority test) as an aid for the assessment of ureter patency comparing to the saline treatment. Below is an example of SAS syntax to implement this analysis.

```
DATA psas;
  Set PSASscore;
  If score in (1, 2) then psasC='1Yes'; else psasC='2No';
Run;
PROC SORT data=psas; BY trt psasC;
PROC FREQ DATA=psas ORDER=DATA;
  TABLES psasC / BINOMIAL(SUP P=0.45 MARGIN=0.05 CL=WILSON) alpha=.05;
  BY trt;
  ODS OUTPUT BinomialCLs=bCL
    BinomialSup=pval
  ;
run;
```

This syntax makes the 'Yes' response to be the first category so the binomial test will examine the proportion of response in the Yes category. The null proportion of 0.45 and margin of 0.05 makes the point estimate of superiority limit to be 0.50 (superiority limit = the null proportion + margin). The 'TRT' is coded to 'High', 'Low' or 'All'. 'All' includes subjects from both IC High and IC Low doses.

An exploratory analysis to examine any difference in PSAS with the use of IC High dose vs the IC Low dose will be performed via a Cochran-Mantel-Haenszel (CMH) test for 'Row Mean Scores Differ'. Below is an example of SAS syntax to implement this analysis

```
PROC FREQ DATA=psas;
  TABLES dose*psas / noproct CMH2 alpha=.05;
  ODS OUTPUT CMH=pval
  ;
run;
```

where 'dose' is coded to Low or High; the 'PSAS' is the satisfaction rating score (1, 2, 3, 4, or 5).

Normal p-value for each analysis will be reported as is without controlling for multiple comparisons.

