5.5.3. Dichotomization of the Difference in Conspicuity

The third approach is to dichotomize the difference in conspicuity between the surgeon and the blinded reader. The four scores from the surgeon will be paired with the four scores from the blinded central reader based on treatment and ureter for a given subject. Based on the difference in the paired conspicuity (see [Section 3.8.5](#)) a concordance response variable will be derived for each pair of the conspicuity:

- a. the ratings are in agreement when the difference in score is (+1, 0, -1), otherwise
- b. the ratings are not in agreement when the difference is more than +/- 1 point

The association of this concordance response variable (agree vs not agree) with treatment and ureter will also be evaluated using the GEE model based on the concept of logistic regression for dichotomized response. In case of missing data that prevent from forming a pair of observations to derive this concordance response variable, the data will be excluded from this analysis.

The score statistics will be used to determine if the treatment is statistically associated with this dichotomized response. The following is an example of SAS syntax for this analysis between the IC Hight dose vs Saline. This analysis will be performed separately for each comparison (IC High dose vs Saline, IC Low dose vs Saline, and IC High dose vs IC Low dose). All subjects with ≥ 1 missing data from either surgeon or central reader will be excluded from this analysis.

```

PROC GENMOD DATA=dischotH descending;
CLASS usubjid ureter(ref='Right') TRT(ref='Saline');
MODEL response (event='Y') = trt ureter trt*ureter
                           /LINK=LOGIT DIST=BINOMIAL TYPE3; (Model 5)
REPEATED subject = usubjid / type=EXCH;
ESTIMATE 'OR: IC vs Saline' trt 1 -1 / exp;
Run;

```

```

PROC GENMOD DATA= dischotH descending;
CLASS usubjid ureter(ref='Right') TRT(ref='Saline');
MODEL response (event='Y') = trt ureter
                           /LINK=LOGIT DIST=BINOMIAL TYPE3; (Model 6)
REPEATED SUBJECT = usubjid / TYPE=EXCH;
ESTIMATE 'OR: IC vs Saline' trt 1 -1 / exp;

```

Where:

1. 'TRT' is coded to IC or Saline
2. 'URETER' is coded to 'Left' or 'Right'
3. 'USUBJID' is the unique Subject Identification
4. REPEATED statement controls the intra-subject correction due to repeated measures. In this example, exchangeable working correlation structure is used (TYPE=EXCH).

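### Averaged central scores can be 3.5 or 4.5, but the responder rule lists the IC score as 3, 4 or 5, so literal coding counts those ureters as non-responders

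*SAP*

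**What the plan says.** **Final score.** Two central readers each score every ureter in every video on the integer scale 1 to 5. When they are within one point, SAP Section 2 says: "In this case, the average score across the two reviewers will be the final score for efficacy analysis". Section 5.1 repeats it: "In this case, the average score across the two reviewers will be the final score from the central reader". Otherwise a third reader's score is used. No rounding rule appears anywhere.

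**Responder rule.** Responder status is a secondary endpoint, taken from the central score and assessed per ureter. Section 5.3 requires IC minus saline of at least 1 "and the conspicuity score following the IC treatment is (3, 4, or 5". Section 2 (secondary objective 3), Section 2.1.1 and Section 3.8.2 use the same list; Section 3.8.2 reads "and the conspicuity score following the IC treatment is (3, 4, or 5) for a subject".

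**Related wording.**
- Section 3.8.3.1 defines the time-to-visualization event by a threshold: "when the conspicuity score is 4 or higher per central reader score for this ureter".
- Section 5.2 codes the satisfaction list as set membership: "If score in (1, 2) then psasC='1Yes'; else psasC='2No".
- Section 5.5.3 uses a list for concordance, "the ratings are in agreement when the difference in score is (+1, 0, -1), otherwise", and Section 3.8.5 makes clear that this list means a range.
- Section 3.8.5 and the model notes in Section 5.1 describe the conspicuity score as taking the values 1 to 5 in whole numbers only.

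**Intervals.** Section 5.3 plans normal-approximation 95% limits for the responder proportions. Section 5.2 uses Wilson limits for satisfaction and says that they perform better than Wald limits.

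**The concern.** The averaging rule and the responder rule do not fit together. Readers scoring 3 and 4, or 4 and 5, are accepted as consistent and do not go to the third reader, so 3.5 and 4.5 are ordinary outcomes of the design. Neither value is on the responder list.

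Taken literally, the rule is not monotone: a better IC score can turn a responder into a non-responder. The reported proportion would then fall because two readers differed by one point, not because the drug worked less well. Two programmers could also report different rates from the same data, one coding membership of the list and the other a threshold.

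What is at stake is a named secondary endpoint with two planned tables (14.2.3.1 and 14.2.3.2). It has no planned test, and Section 3.4 limits type I error control to the primary endpoint, so the primary conclusion is not at risk.

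**Working it through.** The documents give no responder rate, no reader-agreement figure and no responder sample size, so there is no stated figure to reproduce.

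**1. Possible final scores.** Integer pairs from 1 to 5 that differ by at most 1 have nine possible averages: 1, 1.5, 2, 2.5, 3, 3.5, 4, 4.5 and 5. A 3.5 arises only from readers at 3 and 4, and a 4.5 only from readers at 4 and 5.

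**2. Combinations that qualify.** There are 9 × 9 = 81 IC/saline pairs. The table applies each reading of the rule to all of them.

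| Reading | Qualifying pairs | Change from the first row |
|---|---|---|
| IC ≥ 3 and gain ≥ 1, unrounded | 25 | – |
| IC in the list {3, 4, 5} and gain ≥ 1, unrounded | 15 | loses 10: IC 3.5 with saline 1 to 2.5 (4 pairs); IC 4.5 with saline 1 to 3.5 (6 pairs) |
| Halves rounded up first | 30 | adds 5: IC 2.5 with saline 1, 1.5 or 2; 3.5 vs 3; 4.5 vs 4 |
| Halves rounded down first | 28 | adds 3: 3 vs 2.5; 4 vs 3.5; 5 vs 4.5 |

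These are counts of possible pairs, which are not equally likely. They are not rates.

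**3. Effect on the rate (assumed inputs).** Let R be the per-ureter rate under IC ≥ 3, and f the share of those responding ureters whose IC score is 3.5 or 4.5. The literal rate is R(1 − f). With R = 80%:
- f = 10%: 0.80 × 0.90 = 72%
- f = 20%: 0.80 × 0.80 = 64%
- f = 30%: 0.80 × 0.70 = 56%

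**4. Subject-level categories in Section 5.3, at R = 80% and f = 20%.**
- Both ureters respond together, half-points independent. Left-or-right is R(1 − f²) = 0.80 × 0.96 = 77%, down from 80%. Both is R(1 − f)² = 0.80 × 0.64 = 51%, down from 80%.
- Ureters independent. Left-or-right is 1 − (1 − 0.64)² = 87%, down from 1 − (1 − 0.80)² = 96%. Both is 0.64² = 41%, down from 0.80² = 64%.

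The both-ureters category is hit hardest under either assumption.

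**5. Interval method.** Section 3.2 leaves 116 − 21 = 95 subjects for efficacy, or 47 to 48 per dose if split equally. Exact binomial coverage of nominal 95% limits, in percent:

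| True p | Normal approximation, n = 47 / 48 | Wilson, n = 47 / 48 |
|---|---|---|
| 0.80 | 91.2 / 92.9 | 93.5 / 95.4 |
| 0.90 | 95.0 / 86.4 | 95.2 / 94.7 |
| 0.93 | 84.5 / 85.3 | 95.6 / 95.2 |
| 0.94 | 93.9 / 94.1 | 97.9 / 97.6 |
| 0.95 | 90.8 / 91.2 | 97.1 / 96.8 |
| 0.97 | 75.8 / 76.5 | 94.8 / 94.4 |

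Coverage jumps from one p to the next, so single values can mislead. Averaged over p from 0.85 to 0.98, it is about 88% for the normal approximation and about 95.5% for Wilson. At 47 of 47 the normal-approximation interval collapses to [1, 1]; the Wilson lower limit is 47/(47 + 1.96²) = 0.92. For 47/47 against 48/48, the normal-approximation interval for the dose difference is [0, 0], while the Newcombe (Wilson-based) interval is [−0.076, 0.074].

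**The case against.** The strongest reply is that few programmers would code the list literally. The concordance variable uses the same averaged score, and there Sections 3.8.5 and 5.5.3 plainly use a list as shorthand for a range. The membership code in Section 5.2 concerns a single whole-number rating, where list and range coincide, so it says little about half-points. A rule that rejects 4.5 against 1 would look odd to anyone who met it in the data, and Listing 16.2.8.2 prints scores beside responder status. All of this makes a threshold the probable intent, as does the fact that both readers' own scores behind a 3.5 or 4.5 are on the list. It does not make the threshold the written rule. Section 3.8.3.1 shows that the SAP can state a threshold when it means one.

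A second reply is that the whole-number descriptions point to an unstated intention to round, which would leave the list correct. But rounding contradicts the averages set out in Sections 2 and 5.1. In either direction it also admits true gains of 0.5, against the explicit requirement of at least 1.

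The remaining objections concern weight. The size rests on assumed R and f; that is so. The interval point is secondary, and at p = 0.80 the gain from Wilson limits is small. No document says that the responder proportion will be high enough for the larger coverage shortfalls to occur. Even so, the change is free, and the SAP already states the preference in Section 5.2.

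**Conclusion.** The concern holds. Followed as written, the responder rule excludes every ureter with an averaged IC score of 3.5 or 4.5, whatever its saline score. That is 10 of the 25 score combinations that a threshold of 3 would accept. It is a fault in a stated definition and does not mean that a miscount is certain to occur, because the sponsor probably intends the threshold.

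The loss in the reported rate is a factor of (1 − f), with f unknown from the documents; the percentages given are illustrations. The damage is confined to the responder tables. The whole-number descriptions of the score are a wording error: the proportional odds model accepts nine ordered levels, and the concordance cut at one point still works with half-points. The definition should be corrected before the responder variable is derived.

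**What to change.** - In SAP Sections 2, 2.1.1, 3.8.2 and 5.3, replace the list with an IC score of 3 or more. State that the level and the gain of at least 1 are both applied per ureter to the unrounded final central score, so 3.5 and 4.5 qualify and 2.5 does not.
- Do not round the averages as a substitute. If the sponsor wants 2.5 to count, the SAP should say so explicitly.
- In Section 3.8.5 and the model notes of Section 5.1, note that the central score can take half-point values.
- In Section 5.3, use Wilson limits for the responder proportions and a Wilson-based interval, such as Newcombe's, for any reported High-minus-Low difference.

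The cost is SAP wording and the matching program lines. No new data are needed, and the primary analysis does not change.
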